#### **2.4.2 Prior and concomitant therapies**

Concomitant medications new or changed since ORION-8 baseline will be summarized by 3rd level Anatomical Therapeutic Chemical (ATC) classification and preferred name. Medications will be coded using the World Health Organization (WHO) drug dictionary.

ORION-8 baseline concomitant lipid modifying therapies (LMT) and LMTs new or changed since ORION-8 baseline will be summarized by preferred name with dose and frequency. LMTs are medications with 2nd level ATC classification being C10 (lipid modifying agents) according to the coding by the WHO drug dictionary. LMTs will be grouped into statins and other LMT. Statins will be further grouped by intensity (low, moderate, high) according to American College of Cardiology/American Heart Association (ACC/AHA) classification of statin intensity and based on the specific statin drug name, dose, and frequency recorded in the data.

ORION-8 baseline concomitant LMT is defined as any LMT started before or on ORION-8 Day 1 and either still ongoing or stopped on ORION-8 Day 1 or later. Any medications/LMT with start date > ORION-8 Day 1 are considered as new or changed concomitant medications/LMT.

### **2.5 Analysis supporting primary objective(s)**

The primary objective of the study is to evaluate:

- The effect of inclisiran treatment on the proportion of subjects achieving prespecified LDL-C targets at EOS.
- The safety and tolerability profile of long-term use of inclisiran. This objective will be addressed in [Section 2.7](#).

#### **2.5.1 Primary endpoint**

The primary efficacy analysis of this study is to assess the proportion of subjects who attain global lipid targets for their level of ASCVD at EOS. Summaries will include the number and percentage of subjects who attain global lipid targets for their level of ASCVD, along with the 95% CI for the percentage. In addition, the proportion of subjects who attain global lipid targets for their level of ASCVD at ORION-8 baseline and at each scheduled visit from Day 90 to Day

1080 will be provided. The analysis will be performed for the Safety Population overall and by treatment group of the feeder studies.

### **2.5.2 Handling of missing values/censoring/discontinuations**

Missing data will not be imputed. Subjects missing any required data for computing the endpoint will be excluded from the analysis.

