10.2.4 Missing Data Handling

Unless otherwise specified, missing data will not be imputed and will be excluded from the associated analysis.

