Subjects moving over from the open-label ORION-3 study will not receive study drug at Day 1. Their first dose of study drug in this trial will be at Day 90. This is to maintain their semi-annual dosing schedule on inclisiran treatment.

After the Day 90 dosing, subjects rolled over from all feeder trials (ORION-3/9/10/11) will return for open-label drug administration of inclisiran sodium 300 mg every 180 days until Day 990. The EOS visit will be on Day 1080. For subjects who discontinued early, the EOS visit should be completed  $\geq 90$  days following the last inclisiran injection whenever possible.

[figure not shown]
The duration that each subject is expected to participate in this study is a maximum of 3 years or the occurrence of one of the following events, whichever occurs first:

- a recommendation of discontinuation by the investigator or Sponsor,
- a decision by the subject to discontinue for any reason,
- an administrative decision is made to end the study. In particular, the decision has been made to end the study after the last subject from ORION-9/10/11 completes the 3-year treatment (or discontinued early). As a result, ORION-3 rollover subjects will have shorter than 3 years of participation in this study.

No formal interim analysis will be performed in this study.

A schematic diagram of the study design is presented in [Figure 1-1](#). Note that the study duration for ORION-3 rollover subjects will be shorter than the three-year duration illustrated in the diagram.

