### 2.1 Data analysis general information

All analyses will be performed by Novartis, [REDACTED]. [REDACTED] The most recent version of SAS available in the statistical programming environment of Novartis will be used for the analysis.

Study-collected data will be summarized by the actual treatment groups of the feeder studies (Phase III Inclisiran-Inclisiran, Phase III Placebo-Inclisiran, ORION-3 Rollover) using descriptive statistics, graphs, and/or raw data listings. Categorical variables will be summarized using counts and percentages. Percentages are based on the number of subjects in the analysis set for whom there are non-missing data, unless otherwise specified. For selected categorical variables, the 95% confidence interval (CI) for the percentage will be calculated using Blaker's method. Continuous variables, including changes from baseline, will be summarized using

descriptive statistics (n (number of non-missing observations), mean, standard deviation (SD), median, first and third quartiles (Q1 and Q3), minimum and maximum). For selected continuous variables, the CI for the mean will be provided.

Absolute change and percent change from baseline will be calculated as follows:

- Absolute change from baseline to Day X = Value at Day X – Baseline value.
- Percent change from baseline to Day X = (Absolute change/Baseline value)\*100%.

For laboratory measurements below the lower limit of quantification (LLQ), LLQ/2 will be used as the numeric value for the measurement. For example, if numeric result is missing in the database and character result is “< 3”, the numeric result should be treated as  $3/2 = 1.5$  during analysis.

Analyses for the final CSR will be conducted after the final database lock (DBL) of the study. The final DBL will be performed after ORION-9/10/11 rollover subjects either complete the Day 1080 visit or discontinue early and will not wait until ORION-3 rollover subjects complete Day 1080 visit. The ORION-3 rollover subjects will have shorter than 3 years of participation in this study, and their EOS visit will be scheduled 90 days after their last dosing visit.

Information regarding DMC analysis will be provided in the DMC charter and a separate DMC SAP/TFL shells.

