### **2.3 Subject disposition, demographics and other baseline characteristics**

#### **2.3.1 Subject disposition**

The following information will be summarized for the Safety Population overall and by treatment group of the feeder studies:

- The number of subjects in each analysis population
- The number of subjects by country and site

- The number of subjects who completed the study and discontinued early, with reasons for discontinuation
- The duration on study (days)
- Protocol deviations and violations of subject restrictions

Completers are defined as subjects indicated in the EOS page of eCRF to have completed the study. This will include ORION-9/10/11 rollover subjects who have completed the Day 1080 visit, and ORION-3 rollover subjects whose study duration is shortened to < 3 years by the administrative decision only.

The duration on study is defined as the number of days from Day 1 of ORION-8 to the date of last recorded contact/participation date in the database.

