## **2.12 Other Exploratory analyses**

No exploratory analyses are planned for this study.

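### The primary end-of-study target-attainment proportion drops every subject without an end-of-study LDL-C, and no planned analysis tests that exclusion

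*SAP*

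**What the plan says.** The primary efficacy endpoint is binary and read at one visit: attainment of the subject's lipid target at EOS (Protocol 3.3; SAP Table 1-1). On missing values and discontinuations, SAP 2.5.2 says only: "Missing data will not be imputed. Subjects missing any required data for computing the endpoint will be excluded from the analysis". SAP 2.1 sets the matching default denominator: "Percentages are based on the number of subjects in the analysis set for whom there are non-missing data". Protocol 10.2.4 agrees: "missing data will not be imputed and will be excluded from the associated analysis".

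For output, SAP 2.5.1 plans this: "Summaries will include the number and percentage of subjects who attain global lipid targets for their level of ASCVD", with a 95% confidence interval. It also plans the same proportion "at ORION-8 baseline and at each scheduled visit from Day 90" to Day 1080. SAP 2.5 contains no sensitivity analysis. SAP 2.12 adds "No exploratory analyses are planned for this study", although that section concerns exploratory work and does not itself rule out a sensitivity analysis.

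Some provisions soften the rule. SAP 2.3.1 reports "The number of subjects in each analysis population" and the reasons for early discontinuation. SAP 1.1 tries to obtain a value from early leavers: "For subjects who discontinued early, the EOS visit should be completed" at least 90 days after the last injection where possible. Protocol 4.4 encourages the EOS visit after discontinuation, but it also rules out replacing withdrawn subjects and any follow-up once a subject has left the trial.

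**The concern.** Participation lasts up to three years, so some subjects will have no EOS LDL-C. Reasons include death, withdrawal of consent, loss to follow-up, and a visit held remotely under the pandemic provision in Protocol 6.1. Excluding them gives an unbiased proportion only if they would have attained the target as often as those measured. No planned analysis examines that assumption, because the by-visit proportions leave out the missing subjects at each visit in the same way.

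With about 3000 subjects the confidence interval will be narrow. It reflects sampling error only, so it can understate the uncertainty in the trial's primary efficacy figure. No test, power calculation or decision threshold depends on that figure.

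**Working it through.** **No figure to reproduce.** The plan states no expected attainment, dropout or precision, and Protocol Synopsis says sample size considerations do not apply. The check therefore asks how much missingness would matter.

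**Inputs**
- N = 2991 enrolled (Protocol, Amendment 2 rationale). ORION-3 was added as a feeder in that same amendment, so N may be larger. The stated maximum is 3300.
- Observed attainment p = 80%, range 70% to 90%: assumed.
- Share with no EOS LDL-C, m = 5% to 20%: assumed.
- Attainment among the missing, q, expressed as a gap g = p − q: assumed.

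**Precision.** Half-width = 1.96 × √[p(1−p) / (N(1−m))]. At p = 80%, m = 10%, n = 2692:
- N = 2991: 1.96 × √(0.16/2692) = 1.51 points. The Blaker interval for 2154/2692 is 78.5% to 81.5%.
- N = 3300: 1.96 × √(0.16/2970) = 1.44 points.

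**Bias.** The proportion over all subjects is (1−m)p + mq = p − mg. The observed-case estimate is p, so its bias is mg. In points, at p = 80% and N = 2991:

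| m | half-width | g = −10 | g = 0 | g = +10 | g = +20 |
|---|---|---|---|---|---|
| 5% | 1.47 | −0.5 | 0 | +0.5 | +1.0 |
| 10% | 1.51 | −1.0 | 0 | +1.0 | +2.0 |
| 15% | 1.55 | −1.5 | 0 | +1.5 | +3.0 |
| 20% | 1.60 | −2.0 | 0 | +2.0 | +4.0 |

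**Missingness at which bias equals the half-width** (solve mg = half-width at that m):

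| N | p | g = 20 points | g = 10 points |
|---|---|---|---|
| 2991 | 80% | 7.5% (223 subjects) | 15.6% (467 subjects) |
| 2991 | 70% | 8.6% | 18.2% |
| 2991 | 90% | 5.5% | 11.4% |
| 3300 | 80% | 7.1% | 14.8% |

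**Extreme bounds at p = 80%, m = 10%, N = 2991.** If all 299 missing subjects are non-attainers: 2154/2991 = 72.0%. If all are attainers: (2154 + 299)/2991 = 82.0%. At m = 20% the bounds are 64.0% and 84.0%.

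**Deaths.** Suppose a share d of all subjects died and is part of the 10%. Removing them from the denominator changes the lower bound to 72.0/(1−d): 72.7% at d = 1%, 74.2% at 3%, 75.8% at 5%. The bound therefore depends on how deaths are treated, which the plan does not address.

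**Timing.** Dosing-visit samples at Days 270 to 990 fall 180 days after the previous scheduled dose (270 − 90). Day 1080 falls 90 days after the last (1080 − 990). Earlier LDL-C values are informative but cannot be carried to EOS without allowing for time since dose. A Phase III rollover last dosed at Day 450 would be 1080 − 450 = 630 days from dosing at the planned EOS.

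**The case against.** The strongest reply is that this is a prespecified rule, identical in both documents, for a noncomparative descriptive study. Early leavers who attend an EOS visit are included, so it is not a completers-only analysis. A reader can already divide the number of attainers by the Safety Population size to get the crude lower bound. Comparing EOS with Day 1080 in the Phase III groups may also give some evidence on early leavers who have an EOS value. All of this stands, and it is why the observed-case analysis should remain primary. What it leaves uncovered is the subjects with no EOS value. For them the planned tables yield only bounds 10 points apart at 10% missing, with no estimate under a plausible assumption.

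A reader might infer more than the documents support:
- **That the estimate is inflated.** The gap could be zero or negative, and the documents give no rate from which to judge.
- **That handling of lipid-therapy changes is a flaw.** SAP 2.4.2 tabulates new or changed therapy without linking it to the endpoint, but SAP 2.5.2 excludes only missing data. A measured EOS value therefore counts whatever therapy preceded it. That is a legitimate choice left unstated.
- **That Protocol 4.4 and 4.4.1 contradict each other.** The first encourages an EOS visit after a prohibited lipid-lowering drug is started; the second says subjects who start another PCSK9 therapy will not be followed up. The second can be read as concerning follow-up after leaving the trial, so the two can largely be read together. The wording still needs reconciling, because it decides whether an EOS value is expected.
- **That a tipping-point analysis is needed.** A descriptive study has no conclusion to tip.

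**Conclusion.** The point holds as a worthwhile, inexpensive improvement. The primary proportion rests on an untested assumption about subjects without an EOS LDL-C, and the narrow interval will not show that uncertainty. Under assumed 80% attainment, bias passes the roughly 1.5-point half-width at about 7.5% missing with a 20-point gap, or about 15.6% with a 10-point gap. Below those levels, or with a small gap, the effect is within sampling error. Only N comes from the documents; attainment, missingness, gap and death rates are illustrations, and the extreme bounds are limits, not predictions. Using 3300 instead of 2991 changes little.

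**What to change.** Keep the observed-case proportion as primary and amend SAP 2.5.2 before database lock:

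1. Tabulate missing EOS LDL-C by reason and feeder treatment group, with deaths shown separately.
2. Print the missing-as-non-attainer percentage as a labelled lower bound, with and without deaths in the denominator.
3. Add one multiple-imputation sensitivity analysis for subjects not known to have died. Measured EOS values are kept; missing LDL-C is imputed at the planned EOS and then compared with the subject's target.
   - Planned EOS is Day 1080 for ORION-9/10/11 rollovers. For ORION-3 rollovers, whose participation is shortened, it is the scheduled EOS 90 days after their last dosing visit.
   - Impute within feeder group, from the visits that group is scheduled to have.
   - Include treatment-discontinuation status and time from last inclisiran dose to the planned EOS.
   - Because few values will be observed long after the last dose, apply a short fixed range of delta shifts to the imputed LDL-C, stated in advance.

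Two minor clarifications belong alongside: state that observed EOS values count regardless of lipid-therapy change, and reconcile the wording of Protocol 4.4 and 4.4.1 on whether an EOS visit is expected after another PCSK9 therapy is started.

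The cost is SAP text and a few tables, since visit LDL-C, dosing dates, deaths and discontinuation reasons are already collected. The drawback is a lower-bound figure less favourable than the primary one. If the database is already locked, the same analyses can be run and labelled post hoc.

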## **2.6 Analysis supporting secondary objectives**

The secondary objectives of this study are to evaluate the effect of inclisiran on:

- LDL-C levels
- Other lipids and lipoproteins

### **2.6.1 Secondary endpoint(s)**

The actual value, absolute and percentage change in LDL-C and other efficacy parameters from feeder study baseline will be summarized over time using descriptive statistics. The 95% CI for the mean absolute and percentage change will also be provided. Other efficacy parameters include total cholesterol (TC), triglycerides, high density lipoprotein cholesterol (HDL-C), and high sensitivity C-reactive protein (hsCRP).

All the parameters will be summarized at feeder trial baseline, at ORION-8 baseline, at each scheduled visit from Day 90 to Day 1080, and at EOS. The exception is that post-baseline hsCRP will be summarized at Day 1080 and EOS only because hsCRP in ORION-8 is only assessed at EOS per protocol.

The analysis will be performed for the Safety Population overall and by treatment group of the feeder studies.

### **2.6.2 Handling of missing values/censoring/discontinuations**

Missing data will not be imputed. Subjects missing any required data for computing an endpoint will be excluded from its analysis.

## **2.7 Safety analyses**

The safety objectives of this study are to evaluate the safety and tolerability profile of long-term use of inclisiran.

Unless otherwise specified, safety evaluations will be performed for the Safety Population overall and by treatment group of the feeder studies.

Safety analyses are based on observed values and missing data will not be imputed.

### **2.7.1 Adverse events (AEs)**

The most recent version of MedDRA before DBL will be used for coding AEs. An AE will be counted as an ORION-8 treatment emergent AE (TEAE) if the AE started on or after ORION-8 baseline or the AE was present prior to ORION-8 baseline but increased in severity on or after

ORION-8 baseline. Since the investigators are required to enter any worsened AE as a separate record, implementation-wise an AE is a TEAE as long as its onset date/time  $\geq$  date/time of ORION-8 baseline.

The following summaries will be presented for ORION-8 TEAEs using number and percentage of subjects with the event:

- Overall Summary of TEAEs
- TEAEs by primary SOC and PT
- TEAEs by PT
- TEAEs by primary SOC, PT, and maximum severity
- TEAEs possibly related to study drug by primary SOC and PT
- Treatment Emergent Serious AEs (TESAEs) by primary SOC and PT
- TESAEs by PT
- TESAEs possibly related to study drug by primary SOC and PT
- TEAEs leading to withdrawal of study treatment by primary SOC and PT
- TEAEs with a fatal outcome by primary SOC and PT

Subject data listings will be presented for AEs with a fatal outcome, SAEs, and AEs leading to drug discontinuation. Those listings will include all AEs in ORION-8 database, regardless of whether they are ORION-8 TEAE.

If more than one event occurred with the same SOC/PT for the same subject, the subject will be counted only once for that SOC/PT, using the most severe occurrence for the summary by severity.

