8.4 Procedure for Adverse Event Reporting

8.4.1 Serious Adverse Events (SAEs)

All SAEs that occur from consent (Day1) through EOS must be reported to Novartis safety within 24 hours of awareness of the event using the provided study specific SAE Report Form. Each SAE must also be recorded on the source documents and on the appropriate page of the eCRF.

The investigator should provide any follow-up information for the event to the Sponsor on an updated SAE Report Form as soon as it becomes available. The Sponsor will contact the investigator, if necessary, to clarify any of the event information or request additional information.

If the investigator is notified of a SAE that occurs post-study period, that he or she wishes to report to the Sponsor (eg, an event suspected to be causally related to investigational product), the event should be reported through the process described above.

Where appropriate, if required by local regulations or procedures, the investigator should report these events to the Institutional Review Board (IRB)/Ethics Committee (EC) and/or national regulatory authority in addition to the Sponsor.

Detailed instructions regarding the submission process and requirements are to be found in the investigator folder provided to each site.

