10.2.3 Analysis Windows

The observational period for the study includes Day 1 (EOS visit in the previous study), the Treatment phase which consists of the first dose (Day 1), Day 90 dose, and subsequent dosing

visits every 180 days until Day 990 and EOS (Day 1080) visit. Any event occurring beyond the defined observational period, even if collected in the e-CRF, will not be included in the planned statistical analysis. However, all data, including that reported after the defined observational period, will be included in the subject data listings.

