10.3.4.1 Adverse Events

The Medical Dictionary for Regulatory Activities (MedDRA) dictionary will be used for coding AEs. An AE (classified by preferred term) occurring during the study drug treatment period will

be counted as a treatment emergent AE (TEAE) either if it is not present at Day 1 of this study or if it is present at Day 1 of this study but increased in severity during the treatment period.

The number (percentage) of subjects reporting TEAEs for each preferred term will be tabulated by system-organ class, by system-organ class and severity, and by system-organ class and relationship to study drug. If more than one event occurred with the same preferred term for the same subject, the subject will be counted only once for that preferred term using the most severe or related occurrence for the summary by severity, or relationship to study drug, respectively.

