### **Last contact/participation date**

The last contact/participation date for a subject is the last available date across all the data collected for that subject. For a subject with a death event, the date of death will be used.

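### The SAP's TEAE rule has a start date but no end date, so a post-study SAE entered in the eCRF would be tabulated although the protocol keeps it for listings (minor)

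*SAP*

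**What the plan says.** **SAP 2.7.1** counts an event as treatment-emergent "if the AE started on or after ORION-8 baseline or the AE was present prior to ORION-8 baseline but increased in severity" from that point on. Because sites enter a worsened event as a new record, the section turns this into a programming rule: "implementation-wise an AE is a TEAE as long as its onset date/time" is no earlier than ORION-8 baseline. No end date is given there or elsewhere in the SAP.

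**SAP 5.1.2** treats an event with a missing or partial onset date as a TEAE unless it can be shown to precede baseline. It makes no check against the end of the study.

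**SAP section 4** reports no change from the analysis in the protocol.

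**Protocol 10.2.3** runs the observational period through "visits every 180 days until Day 990 and EOS (Day 1080) visit". It then says: "Any event occurring beyond the defined observational period, even if collected in the e-CRF, will not be included in the planned statistical analysis". The late data are kept, since all data, "including that reported after the defined observational period, will be included in the subject data listings".

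**Protocol 10.3.4.1** also ties TEAEs to a period. Its definition opens "An AE (classified by preferred term) occurring during the study drug treatment period will" and goes on to the new-or-worsened condition.

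**Protocol 8.4.1** requires SAE reporting from consent through EOS. After that it is discretionary: "If the investigator is notified of a SAE that occurs post-study period, that he or she wishes to report to the Sponsor", the event goes through the same process as on-study SAEs. Suspected drug causality is given as an example. Protocol 8.4.2 collects non-serious events through EOS only.

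**SAP 2.1.1** defines the last contact date as the latest date in any data for the subject, and adds: "For a subject with a death event, the date of death will be used".

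**The concern.** Safety is one of the two primary objectives, and it is assessed by counts and percentages of subjects with TEAEs. Up to EOS, collection is complete by design. After EOS, the protocol provides no systematic collection of new events, and what arrives depends on whether an investigator hears of an SAE and wishes to report it. The protocol foresaw that such records might be in the database and kept them out of the tables. A programmer who follows SAP 2.7.1 would put them in.

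The tables would then combine complete follow-up with an incomplete, discretionary tail. Late events would add to numerators while the denominator, the Safety Population, stays fixed. The tables would also differ from the protocol's analysis without any declaration in SAP section 4. The most exposed summaries are serious, related and fatal TEAEs, and the AESI and MACE tables built on the same definition. One further effect is that a reported death after EOS would lengthen that subject's duration on study (SAP 2.3.1), which has no cap.

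**Working it through.** The plan states no figure on this point, so there is none to reproduce. The check applies both rules to the same events and then sets a scale.

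**1. The two rules.** Let *d* be the study day of onset, with baseline at Day 1.
- SAP 2.7.1: TEAE if *d* ≥ 1.
- Protocol 10.2.3: in the analysis if 1 ≤ *d* ≤ the subject's EOS day. The protocol names Day 1080. For early discontinuation I use the subject's own EOS visit.

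| Onset day | EOS day | SAP rule | Protocol window |
|---|---|---|---|
| −5 | 1080 | not a TEAE | outside |
| 500 | 1080 | TEAE | inside |
| 1080 | 1080 | TEAE | inside |
| 1120 | 1080 | TEAE | outside |
| 700 | 540 (early) | TEAE | outside |

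The rules differ only after EOS, and there they always differ.

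**2. Can such a record reach the tables?** Protocol 8.4.1 sends a discretionary post-study SAE through the process for on-study SAEs, and that process includes an eCRF entry. Protocol 10.2.3 mentions late events held in the eCRF. The route is therefore open, but the documents do not show how often, if ever, it is used.

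**3. Scale.** Added percentage points = 100 × *k*/*N*, where *k* is the number of subjects counted only because of a late event. *N* = 2991 is the enrolment at February 2020 (protocol, Amendment 2 rationale), before ORION-3 was added as a feeder. *N* = 3300 is the protocol maximum. The values of *k* are assumptions.

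| *k* | *N* = 2991 | *N* = 3300 |
|---|---|---|
| 1 | 0.033 | 0.030 |
| 2 | 0.067 | 0.061 |
| 5 | 0.167 | 0.152 |
| 10 | 0.334 | 0.303 |
| 30 | 1.003 | 0.909 |

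SAP 2.7 also tabulates by feeder-study group. The documents do not give group sizes. Within a group of size *n* each added subject counts *N*/*n* times as much.

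**4. Opportunity time.** Enrolment ran from April 2019 to February 2020. Assuming mid-month dates, 15 Apr 2019 + 1079 days = 29 Mar 2022 and 15 Feb 2020 + 1079 days = 29 Jan 2023, a difference of 306 days. Across all dates in those months the range is 277 days (30 Apr 2019 to 1 Feb 2020) to 334 days (1 Apr 2019 to 29 Feb 2020). This is the time between the earliest Phase III completer's EOS and the last one's, so it shows only that late reports could arrive before lock.

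**5. Exposure.** SAP 2.4.1 ends exposure at the earlier of last contact and last dose + 180 days. For a last dose on Day 990 the cap is 990 + 180 = Day 1170, which is 90 days after Day 1080. Duration on study has no such cap.

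**The case against.** The best defence is that the protocol still governs. SAP section 4 declares no change, so the exclusion in protocol 10.2.3 could be read into SAP 2.7.1. But 2.7.1 gives an explicit programming rule that does not apply the exclusion, and 5.1.2 repeats the one-sided test. A programmer should not have to infer the upper bound.

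Three further points stand, and they limit the size of the issue:
- The analysis is descriptive and non-comparative, so no test or decision depends on the bound.
- SAP 2.7.1 lists all SAEs and fatal events whatever their TEAE status, so late events remain visible. Counting them would raise reported incidence and would not hide harm.
- Protocol 4.4 bars further information-gathering after discontinuation from the trial, which narrows the inflow.

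A fair objection also applies to a careless remedy. If the window closed at the last visit for subjects without an EOS visit, on-study deaths and SAEs between visits 180 days apart would be lost. If it closed at the SAP's own last contact date, the bound would be circular, because a late report moves that date. Also, protocol section 6 lets the visit at which a subject stops become the EOS visit, so an EOS bound can exclude events within the 180 days after the last dose that SAP 2.4.1 counts as exposure. That follows from the protocol's window. Those events would stay in the listings.

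**Conclusion.** The inconsistency is real and minor. SAP 2.7.1 and 5.1.2 would count events that protocol 10.2.3 excludes from the tables, and SAP section 4 does not disclose this. The size is unknown. At about 0.03 percentage points per added subject, overall TEAE percentages would hardly move, while sparse rows such as related or fatal serious events could change visibly with a few late reports. This assumes that at least some post-study SAEs are entered in the eCRF before lock.

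A reader might infer four stronger claims that the documents do not support:
- **That such SAEs do enter the tables.** Entry is possible, but neither certain nor shown to be routine.
- **That the late events are selected for suspected causality.** Causality is only the example in protocol 8.4.1. What is established is that reporting is discretionary.
- **That 306 days, or 28% of 1080 (306/1080), measures a bias.** It is a calendar gap for the earliest enrolled subjects. It is neither a count of events nor a share of the data.
- **That the last contact rule distorts incidence through follow-up time.** The TEAE summaries are percentages of subjects, with no person-time. Exposure-adjusted rates appear in the SAP's abbreviation list, but no section specifies one, and exposure is already capped. The rule affects only duration on study.

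**What to change.** In SAP 2.7.1, require onset on or after ORION-8 baseline and on or before the end of the subject's observational period. Define that end as:
- the EOS visit date; or
- for a subject with no EOS visit, the date of death on study or the date of study discontinuation recorded on the eCRF EOS page.

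This keeps on-study deaths and SAEs between visits in the tables. The SAP refers to that page for completion status but does not say which dates it holds, so the sponsor should confirm that a discontinuation date is there.

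In 5.1.2, keep the present default for incomplete dates, but also exclude an event when there is enough information to show that it began after that end date. Present later events in listings only. Apply the same end date to duration on study in 2.3.1. Exposure needs no change.

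If the sponsor prefers to count later events, SAP section 4 should declare and justify this, and the tables should show them separately from events through EOS.

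The cost is one definition, one date condition in the programs and a matching line in 5.1.2. No data are lost. The SAP is a first version dated 04-Jul-2022, before database lock, so the change could have been made before the tables were run.
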